C.1. Study design. This is a double-blind, 4-intervention, 4-period crossover randomized controlled trial of HFOx, HFAir, LFOx, and LFAir in non-hypoxemic cancer patients (**Figure 3**). We plan to enroll 36 patients in total. The eligibility criteria are listed in **Table 1**. We will use a computer-generated sequence for randomization. Even with 2 different flow rates, patients and research staff will be blinded to the gas (i.e., oxygen v. air) while a separate respiratory therapist will provide the study intervention; thus, this will remain a double-blind study. On the basis of our experience conducting symptom control trials, we believe this study design will not be an undue burden for hospitalized patients (approximately 1-2 hours, including washout).¹⁹ The rationale for the current study design is as follows:

[figure not shown]

Figure 3. Study Flow Chart. In this double-blind, 4-intervention, 4-period crossover randomized controlled trial, all patients will try 10 minutes of each intervention, followed by a variable washout period (purple arrow). The sequences above represent one of the 6 Latin Squares that may be used.

- **Crossover design**—This design allows intra-individual comparison, thus maximizing study power (144 tests in 36 patients) in addition to providing overall preference.²⁰ We use the Latin square design to minimize the sequences needed.
- **Intervention duration**—We will limit this intervention to only 10 minutes in this proof-of-concept study to minimize study burden and attrition, and to examine the effect of short intervention. We expect the effect of gas exchange to be rapid. Previous dyspnea studies with oxygen delivery have utilized similar durations⁸.
- **Variable washout period**—although the washout period is expected to be short (<10 min), it has not been defined. Thus, we will measure dyspnea on the Numeric Rating Scale starting after 10 minutes of each intervention every 5 minutes until patient returns to within 1 point of the baseline level of dyspnea (i.e. immediately prior to starting the first intervention) before we proceed to the next intervention.
- **Inclusion of HFOx, HFAir and LFAir arms**—HFOx has not been tested in non-hypoxemic cancer patients. No published study has examined the therapeutic role of HFAir in any patient population. The efficacy of LFAir has not been studied in the hospitalized population²¹.

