- **Use of LFAir as control**—LFAir at 2 L/min is a well-accepted control intervention in published studies.

C.2. Eligibility criteria. The eligibility criteria are shown in Table 1. The rationale for including patients with obstructive and restrictive lung disease in this study is that the mechanisms of dyspnea relief (e.g., trigeminal nerve stimulation and decreased breathing effort; see Figure 1) are applicable to both types of pulmonary disorder.

Table 1. Study Eligibility Criteria

Inclusion Criteria

1. Diagnosis of cancer
2. Patients seen by palliative care, thoracic oncology, pulmonary medicine, or emergency care at MD Anderson Cancer Center
3. Dyspnea Numeric Rating Scale at rest ≥ 3 of 10 (average over last 24 hour)
4. Non-hypoxemic (i.e. oxygen saturation $>90\%$ on ambient air)
5. Able to communicate in English or Spanish
6. Age ≥ 18 years
7. Able to tolerate high-flow oxygen/air

Exclusion Criteria

1. Memorial Delirium Rating Scale >13
 2. Hemodynamic instability
 3. Respiratory failure requiring mechanical ventilation or non-invasive ventilation
 4. Frequent use of rescue opioids $>8x/day$ or rescue bronchodilators $>8x/day$ over last 24 hours
 5. Currently requiring high flow oxygen for oxygenation
-

C.3. Recruitment. Patients seen by the supportive care team, thoracic oncology, pulmonary medicine, or emergency care will be screened for this study. The supportive care inpatient consultation team sees 80 patients (10-20 new consults) per day. A two-step consent process will be used. First, verbal consent will be obtained by the study staff before screening potential participants to determine their eligibility. Before signing any consent document, a respiratory care therapist will allow patients a trial of high-flow oxygen/air to ensure tolerance of high flow. Eligible patients will be formally enrolled in the study after they have signed the informed consent form indicating their willingness to participate in the trial. Once enrolled, the research staff will work with the patient to identify ideal time to conduct the study. We will document the number of patients who are screened, approached, eligible, enrolled, and randomized for the study and the number who complete it. When patients complete study procedures, they will be compensated with a \$25 gift card as a show of appreciation for their time and participation. Patients' reasons for declining to participate will also be captured.

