C.4. Randomization. Randomization will be performed immediately before the patient is ready to start study procedures by our study respiratory therapist using the Clinical Trial Conduct website (<https://biostatistics.mdanderson.org/ClinicalTrialConduct>), which is maintained by the Department of Biostatistics at MD Anderson. The trial statistician will train the respiratory therapists in the use of this website for randomizing patients. We will use a computer-generated sequence in permuted blocks to randomize patients, in a 1:1:1:1 ratio, to the four treatment sequences from a Latin square. Each sequence has a specific order of high flow oxygen, low flow oxygen, high flow air, and low flow air.

C.5. Study interventions. Respiratory therapists will use a high flow oxygen device to deliver HFO₂. This device was approved by the U.S. Food and Drug Administration in 2007 (K033710) to add "moisture to, and to warm, the breathing gases for administration to a patient. Gases available for medical use do not contain sufficient

moisture and may damage or irritate the respiratory tract, or desiccate secretions of patients whose supraglottic airways have been bypassed. This may be indicated for patients requiring mechanical ventilation, positive pressure breathing assistance, or general medical gases". HFO₂ will be delivered via nasal prongs. The flow of oxygen will be maximized (set between 20 and 60 L/min), if tolerated, to minimize dyspnea. The FiO₂ will be set at 100%. The level of heat will be adjusted to keep the patient comfortable. HFAir will also be delivered by Optiflow in an identical manner to HFO₂, except that we will use pressurized air instead of oxygen. LFO₂ and LFAir will be provided at 2 L/min using a nasal cannula. This flow rate is based on the results of a previous large randomized controlled trial of oxygen use in non-hypoxemic patients²¹. A respiratory care specialist will be present throughout the study period. We have previously collaborated with the same team of respiratory care specialists on other research projects on high-flow oxygen delivery.

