C.6. Blinding. The patients and research staff will be blinded to the assignment of the gas (i.e., oxygen vs. air). The gas will be delivered via gas outlets inside the patient's room, located behind the bed. Only the respiratory therapist administering the gas will be aware of its identity. To ensure proper blinding, the research staff will step out of the room while the respiratory therapist sets up the gas delivery device. The gas supply will be covered with a piece of cloth to ensure proper concealment. The respiratory care specialist will be specifically asked to not to discuss the identity of the study gas. We will assess blinding by asking the patients and study staff about the identity of the gas at the end of study. The flow rate cannot be blinded in this study.

C.7. Study outcomes. See Table 2 for a detailed description of the study assessments. We will also collect data on patient demographics and study feasibility outcomes (rates of enrollment and attrition). The study interventions will be provided to patients while at rest, and dyspnea ratings will only be assessed when patients are at rest.

C.8. Co-interventions. We expect that co-interventions will be minimal because of the short study period. We will document any regularly scheduled, bronchodilators or opioids given 1 hour before or during the study period. However, if patients required as need opioids (for pain or any other reasons) or bronchodilators during the study period, they will need to come off study and will need to be replaced.

C.9. Training of research staff. An orientation will be held with all research staff involved in this study to introduce them to the study design and standardize the provision of each intervention. Particular attention will be paid to ensuring that research staff provide patients with proper instructions so they understand the study assessments. We will also have several mock-ups for practicing the study procedures.

C.10. Data Safety Monitoring Board (DSMB). The MD Anderson DSMB will be providing monitoring for patient safety and data quality assurance purposes.

C.11. Dropouts. Patients will come off study if (1) they decide for any reason to stop; (2) they did not achieve within 1 point of the baseline level of dyspnea after 1 hour during the washout period, (3) they require as need opioids (for pain or any other reasons) or bronchodilators during the study period. These individuals will need to be replaced.

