C.12. Stopping rule. This is a short study and we expect limited attrition. We will stop the study at patient request or if patients required as need opioids (for pain or any other reasons) or bronchodilators during the study period.

Table 2. Summary of Study Assessments

	Baseline	Intervention	Washout period	End of study
Demographics and baseline data ¹	✓	-	-	-
Dyspnea numeric rating scale (<1 min) ²	✓	0, 5, 10 min	q5min	-
Dyspnea Borg scale – intensity and unpleasantness (<1 min) ³	✓	0, 5, 10 min	q5min	-
Physiologic variables (5 min) ⁴	✓	0, 10 min	-	-
Blood pressure	✓	-	-	✓
Adverse effects (<1 min) ⁵	-	0, 10 min	-	-
Length of washout (5+ min) ⁶	-	-	✓	-
Device settings ⁷	✓	✓	-	-
Blinding, preference (<1 min) ⁸	-	-	-	✓

¹ We will collect birthdate, sex, race, cancer diagnosis, co-morbidities, dyspnea cause and baseline, Karnofsky Performance status, the frequency of use of scheduled and as-needed opioids, steroids, and bronchodilators in the 24 hours before and during the study. Validated questionnaires that will be assessed at baseline include the Edmonton Symptom Assessment Scale (measures 10 symptoms [pain, fatigue, nausea, depression, anxiety, drowsiness, shortness of breath, appetite, sleep, and well-being] using numeric rating scales ²²) and the Cancer Dyspnea Scale (12-item questionnaire to assess the quality of dyspnea in cancer patients during the previous few days ²³. Each item has a score between 1 and 5, for a maximum of 60). Bedside spirometry will be performed at baseline using the MicroLoop spirometer (Micro Direct, Inc., Lewiston, ME) according to published guidelines (Miller et al. 2005). This device was approved by the American Thoracic Society and US FDA. Various spirometry parameters will be documented, including, forced expiratory volume in 1 second, forced vital capacity, forced expiratory volume//forced vital capacity, peak inspiratory flow, and peak expiratory flow. We will also assess maximal inspiratory pressure using the NS 120-TRR NIF Monitor (Instrumentation Industries Inc., Bethel Park, PA) according the American Thoracic Society Guideline ²⁴.

² Dyspnea intensity assessed by Numeric Rating Scale is the primary measure. It is a 0 (no dyspnea) to 10 (worst dyspnea) categorical scale validated for rating the severity of dyspnea²⁵⁻²⁷.

³ The intensity of and unpleasantness associated with dyspnea will be assessed using the Borg scale, a validated ratio scale that ranges from 0 (no dyspnea) to 10 (worst dyspnea).^{25,27}

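### Should entry require a resting dyspnea score of at least 3 at the session itself, and not only as a 24-hour average?

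*Combined protocol and SAP*

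**What the plan says.** - **Entry (C.2, Table 1, item 3):** "Dyspnea Numeric Rating Scale at rest ≥ 3 of 10 (average over last 24 hour".
- **Timing (C.3):** the session is arranged after consent: "Once enrolled, the research staff will work with the patient to identify ideal time to conduct the study". No maximum interval is given.
- **Randomisation (C.4):** "Randomization will be performed immediately before the patient is ready to start study procedures". No dyspnea condition is attached.
- **Washout reference (C.1):** each washout lasts until the NRS is "within 1 point of the baseline level of dyspnea (i.e. immediately prior to starting the first intervention" reading. That reading serves as a reference and is not an entry condition.
- **Measurement (C.7 and Table 2):** "dyspnea ratings will only be assessed when patients are at rest". The NRS is taken at baseline, at 0, 5 and 10 minutes of every intervention, and every 5 minutes in washout. Of the scale, Table 2 says "It is a 0 (no dyspnea) to 10 (worst dyspnea) categorical scale".
- **Objective and analysis (A.1, D.1):** preliminary effect sizes, from the slope in a mixed model and the mean 10-minute change for each intervention.

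Nothing in C.11, C.12 or D.1 adds a minimum current score.

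**The concern.** Entry rests on a day-long average and the outcome on a moment. Dyspnea varies within the day: B.1 says that more than 80% of patients with dyspnea have breakthrough episodes, particularly on exertion, and these sessions involve no exertion. A patient who averaged 3 or 4 over a day could therefore be at 0 or 1 when the first gas is started.

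Two things would then be at stake. First, an NRS cannot fall below 0, so the largest possible improvement equals the starting score. The more effective intervention meets that limit sooner, which pulls between-intervention differences toward zero, and estimating those differences is why the trial is run. Second, from a baseline of 0 or 1 a fall to 0 already counts as returned to baseline, so for that patient the washout rule tests nothing and the recorded washout time says little.

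**Working it through.** **The plan's own figure.** D.2 computes one interval: 64% to 92% for 80% completion in 36 patients. The exact binomial interval for 29/36 (80.6%) is 64.0% to 91.8%, so it reproduces. It uses no NRS values and does not depend on the entry rule. D.2 gives no SD, target effect or precision for the NRS.

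**What a given start allows.** Take a uniform fall of 1.9 points (B.3). It comes from two-hour use in patients of whom 93% were hypoxemic, so it is illustrative only. Observable fall = min(start, 1.9):

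| Start | Observable fall | Lost |
|---|---|---|
| 0 | 0 | 1.9 |
| 1 | 1.0 | 0.9 |
| 2 or more | 1.9 | 0 |

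Benefit is invisible only at 0 and capped at 1. At 2 a fall of this size still fits.

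**How often patients start low (assumptions).** 24-hour averages are normal with centre 4.5 or 6 and SD 1.5 or 2, truncated to 3-10. The momentary score adds noise with SD 1 or 2, rounded and held to 0-10. There are eight scenarios, each with 1,000,000 simulated patients.

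| First-period start | Range over scenarios | Of 36 patients |
|---|---|---|
| Below 3 | 1.5-14.8% | 0.5-5.3 |
| 0 or 1 | 0.2-6.8% | 0.1-2.4 |
| 0 | 0.0-2.6% | 0-0.9 |

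**Loss from the floor** = 1.9 × P(start 0) + 0.9 × P(start 1).

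- Worst scenario (centre 4.5, SD 1.5, noise SD 2): P(0) = 0.0261 and P(1) = 0.0678 − 0.0261 = 0.0417. Loss = 0.0496 + 0.0375 = 0.087 point; 0.087/1.9 = 4.6%.
- Mildest scenario (centre 6, SD 1.5, noise SD 1): P(0) = 0.0001 and P(1) = 0.0018. Loss = 0.0018 point, or 0.1%.

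**Later periods.** The washout rule lets these begin one point lower. As an extreme bound, put every patient one point down in the worst scenario, with P(2) = 0.1478 − 0.0678 = 0.0800. Loss = 1.9 × 0.0678 + 0.9 × 0.0800 = 0.20 point.

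**Individual falls that vary (assumed SD 2).** Truncation then reaches higher starts. In the worst scenario, for two interventions with mean falls of 1.9 and 0.9, the observed difference is 0.86 (SD 2.56) with the present rule and 0.92 (SD 2.67) if every start is at least 3. The raw difference is about 7% smaller (0.86/0.92 = 0.93). Relative to its SD it hardly moves: 0.86/2.56 = 0.33 against 0.92/2.67 = 0.35.

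**Against the trial's precision.** With an assumed paired-difference SD of 1.5 to 2.5, the 95% half-width in 36 patients is 2.03 × SD/6, or 0.51 to 0.85 point. The earlier trial's interval (B.3) was 0.4 to 3.4. Every loss above, including the 0.20 bound, is smaller than that half-width.

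**The case for a change.** The strongest case for a change is that the gap is real and cheap to close. The baseline NRS takes under a minute and randomisation already happens at the session, so checking for a current score of 3 would add one question. Other features of the plan make low starts plausible. Scheduled opioids or bronchodilators in the preceding hour are recorded but not restricted (C.8). Patients who need as-needed doses during the session leave and are replaced (C.8, C.11). A high-flow tolerance trial comes before consent with no stated gap (C.3), and B.3 reports two patients with scores of 2 or less up to an hour after high flow. A patient averaging exactly 3 has a 31-42% chance of scoring 2 or less at a given moment (assumed momentary SD 1 to 2.5), and then 79-96% of a 1.9-point fall is visible. If benefit is taken as 40% of the starting score, the mean effect is 1.97 for all patients against 2.22 for those starting at 3 or more, 11% less.

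Part of this stands: low starts can occur, and in those patients the washout rule is uninformative. The size does not carry over to the trial. The exact-3 patient is the extreme of the eligible range; at an average of 5, at least 94% of the fall is kept. The 1.97 against 2.22 comparison contains no floor at all. It shows that selecting higher scores raises their mean, as any higher cutoff would, so it measures enrichment and not bias.

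Nor is the requirement free. Postponing until the score reaches 3 selects momentary highs. A second reading a few minutes later removes measurement noise but not an episode that is still subsiding, so the mean 10-minute change within each intervention, a planned output, could be inflated. Returning to within 1 point of a high baseline would be harder, and C.11 removes patients who have not returned after an hour. Sessions in inpatients would be delayed, and the population would shift from patients with persistent resting dyspnea to patients caught at a worse moment.

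**Conclusion.** The reading of the text is right: entry uses a 24-hour average and no minimum current score applies at the session. No change follows. Under the assumed distributions, at most about 2 or 3 of 36 patients start at 0-1 and a uniform 1.9-point effect loses 0.1-4.6% in the first period. With variable individual falls, the raw difference between interventions is about 7% smaller in the worst scenario, and its ratio to the SD is almost unchanged. Comparisons are within patient and the sequence is randomised, so the floor weakens differences and does not create one in favour of an intervention.

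These sizes rest on NRS distributions and SDs that the documents do not give; lower averages or wider swings within the day would raise them. Choosing between a 24-hour average and a current-score requirement trades who is studied against some sensitivity, and either is defensible in a trial seeking preliminary estimates. The NRS at baseline and at minute 0 of each period is already collected, so analysts can report the starting scores and look at results by starting score without any change to the plan.

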⁴ Heart rate, respiratory rate, oxygen saturation, and transcutaneous CO₂ level will be measured.

⁵ Dry eyes, dry nose, nasal moisture and anxiety will be assessed using a numeric rating scale from 0 (not at all) to 10 (worst possible).

⁶ Dyspnea intensity will be assessed using the NRS scale every 5 minutes until patients return to baseline. The duration of washout is a useful secondary outcome.

⁷ FiO₂, flow rate, and temperature.

⁸ We will assess blinding (oxygen v. air) of patients and research staff after each treatment. At the end of the study, patients will be asked which of the 4 interventions they prefer

D. STATISTICAL CONSIDERATIONS

D.1. Analysis plan.

Design: We propose a 4-period, 4-intervention balanced Latin-square cross-over (Williams) design with 4 sequences and 36 patients (i.e., 9 replicates per sequence). The primary outcome is the Dyspnea Numeric Rating Scale (0-10). Each intervention is 10-minutes long with NRS assessments at 0, 5 and 10 minutes. Washout periods between interventions will continue until NRS assessment returns to within one unit of baseline.

Primary analysis: We will fit a mixed effects linear model to the Dyspnea Numeric Rating Scale data to account for the repeated measurements (i.e. 0, 5 and 10 minutes) which yield period, sequence, and carryover effects and to model the various inter-patient and intra-patient sources of variation. Appropriate data visualization and residual analyses will also be performed. The primary objective of the study is to obtain preliminary estimates of the effect sizes (In a mixed model, the slope of change will provide an estimate of effect size. We will also determine the mean change in NRS over 10 minutes for each study intervention).

Secondary analysis #1: We will estimate the completion rate as the proportion of patients starting treatment that complete all four interventions.

Additional secondary analyses: Using mixed effects linear models we will obtain preliminary estimates of the study effects for physiologic function (oxygen saturation, respiratory rate, transcutaneous CO₂). We will also assess washout period duration in a similar fashion. Finally, we will tabulate patient intervention preferences obtained at the end of the study.

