D.2. Sample size justification. We will enroll 36 patients over 2 years. Although due to the complexity of the statistical models we cannot accurately estimate the precision of our effect estimates, based on our experience with mixed effects models, 36 patients with 12 repeated measurements (3 times for each of 4 interventions) will provide adequate precision. If the completion rate is 80% then with 36 patients, a 95% confidence interval on this estimate would extend from 64% to 92%.

E. DATA CONFIDENTIALITY PROCEDURES

Study data will be collected and managed using REDCap (Research Electronic Data Capture) tools hosted at MD Anderson or hardcopy surveys. Participants will have the option to complete surveys electronically or hardcopy. Data entry of any hardcopy survey will be completed using REDCap software. REDCap (www.project-redcap.org) is a secure, web-based application with controlled access designed to support data capture for research studies, providing: 1) an intuitive interface for validated data entry; 2) audit trails for tracking data manipulation and export procedures; 3) automated export procedures for seamless downloads to common statistical packages; and 4) procedures for importing data from external sources. In the case of multi-center studies REDCap uses Data Access Groups (DAGs) to ensure that personnel at each institution are blinded to the data from other institutions. REDCap (<https://redcap.mdanderson.org>) is hosted on a secure server by MD Anderson Cancer Center's Department of Research Information Systems & Technology Services.

REDCap has undergone a Governance Risk & Compliance Assessment (05/14/14) by MD Anderson's Information Security Office and found to be compliant with HIPAA, Texas Administrative Codes 202-203, University of Texas Policy 165, federal regulations outlined in 21CFR Part 11, and UTMDACC Institutional Policy #ADM0335. Those having access to the data file include the study PI and research team personnel. Users are authenticated against MDACC's Active Directory system. All protected health information (PHI) will be removed from the data when it is exported from REDCap for analysis. Following publication study data will be archived in REDCap.

Health information will be protected and we will maintain the confidentiality of the data obtained from the patient's chart.

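### Washout duration goes into a linear mixed model, but C.11(2) cuts washouts at 60 minutes and the plan has no rule for those that reach the limit

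*Combined protocol and SAP*

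**What the plan says.** C.1 has the dyspnea NRS repeated every 5 minutes after each intervention until it is within 1 point of the level recorded just before the first intervention. It expects washout to take under 10 minutes but says the length is not established. Footnote 6 to Table 2 names washout duration as a secondary outcome. D.1 says washouts go on until the score is within one unit of baseline, and that duration will be assessed in the same way as the physiologic outcomes, that is, by a linear mixed model.

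The limit appears only in C.11. Patients come off study if "they did not achieve within 1 point of the baseline level of dyspnea after 1 hour during the washout period", if they decide to stop, or if they need as-needed opioids or bronchodilators. For all three reasons: "These individuals will need to be replaced".

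For the primary outcome, D.1 says "We will fit a mixed effects linear model to the Dyspnea Numeric Rating Scale data" and adds "We will also determine the mean change in NRS over 10 minutes for each study intervention". It names no analysis set. The planned counts are "144 tests in 36 patients" (C.1), "4 sequences and 36 patients (i.e., 9 replicates per sequence" (D.1) and "36 patients with 12 repeated measurements (3 times for each of 4 interventions) will provide adequate precision" (D.2).

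**The concern.** D.1 treats washout duration as if every washout ends in a return to baseline. Under C.11(2) some cannot: at 60 minutes the patient leaves and the true duration is known only to exceed 60. These are by definition the longest washouts. A linear mixed model copes with values missing for reasons unrelated to the missing value, but here the value is missing because it is large. Leaving it out, or recording 60, pulls the mean down, and pulls it down most for whichever intervention has the longest-lasting effect.

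C.1 says the washout length has not been defined, so this trial will be a source for it. A mean that is too short could lead a later crossover trial to plan too short a washout.

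A lesser matter is that C.11 replaces these patients, and D.1 does not say whether the periods they had already completed stay in the primary model.

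**Working it through.** **1. The plan's own figure.** D.2 states: "If the completion rate is 80% then with 36 patients, a 95% confidence interval on this estimate would extend from 64% to 92"%. The exact (Clopper-Pearson) interval for 29 of 36 is 64.0% to 91.8%, which matches. For 36 finishers among 36/0.80 = 45 starters it is 65.4% to 90.4%, which does not. So D.2 counts 36 as starters there. With 29 finishers and 7 non-finishers giving at most three periods each, at most 29×4 + 7×3 = 137 tests exist, against 36×4 = 144 in C.1. This bears only on the minor clarification.

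**2. Washout duration.** Inputs: a 60-minute limit (C.11); washout expected under 10 minutes (C.1). Assumption, not in the documents: durations are exponential with mean m, so r = P(over 60) = exp(−60/m) and m = 60/(−ln r).

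- Over-60 washouts dropped: expected mean = m − 60r/(1 − r).
- Over-60 washouts entered as 60: expected mean = m(1 − r).

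| r | True mean (min) | Dropped | Entered as 60 |
|---|---|---|---|
| 0.25% (m = 10) | 10.0 | 9.85 (1.5% short) | 9.98 (0.25% short) |
| 2% | 15.3 | 14.1 (8% short) | 15.0 (2% short) |
| 5% | 20.0 | 16.9 (16% short) | 19.0 (5% short) |

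Example at r = 5%: m = 60/2.996 = 20.0; dropped, 20.0 − 60×0.05/0.95 = 20.0 − 3.2, which is 16.9 before rounding; entered as 60, 20.0×0.95 = 19.0.

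Three washouts fall between four interventions, so 36×3 = 108 are at risk. At m = 10, 108×0.0025 = 0.27 would be expected to reach the limit; at r = 2%, about 2; at r = 5%, about 5.

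**3. Primary outcome, if only completers were analysed.** The plan does not say this will be done. Assumed: mean improvement 1.9 on high flow (B.3's figure for HFOx) and 0.5 on low flow; SD 1.5 between and 2.0 within patients. Exit can follow periods 1 to 3, with a fixed chance q after a change of 1.5 or more in either direction, since C.11(2) applies to both. Here r is the chance of exit through lasting relief after a high-flow period. The total SD is √(1.5² + 2.0²) = 2.5, so the probability of an improvement of at least 1.5 is Φ(0.4/2.5) = 0.564 and q = r/0.564. Exits through worsening come on top.

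| r | HFOx mean change, completers only (true 1.90) | Short by |
|---|---|---|
| 2% | 1.88 | 1% |
| 5% | 1.83 | 4% |
| 10% | 1.76 | 7% |
| 15.4% | 1.67 | 12% |

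At the far end the HFOx minus LFAir contrast is 1.33 against a true 1.40, or 5% short. For scale, the standard errors with 36 patients are √(2×2.0²/36) = 0.47 for the contrast and 2.5/√36 = 0.42 for the mean change.

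**The case against.** The strongest reply is that the problem may hardly arise. If the mean washout is 10 minutes or less, fewer than one washout in the whole trial is expected to reach the limit, and the shift is far below anything that matters. Washout duration is not among the objectives in section A, the trial seeks preliminary estimates, and the 1-hour limit protects later periods from carryover and limits the burden on inpatients. All of this stands. It limits the weight of the point, but D.1 still describes an analysis that does not match C.11.

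A reader might go further in two ways, and the documents support neither.

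- **That replaced patients' data will be discarded.** D.1 fits the model to the NRS data without restricting it to completers, and such a model can use incomplete patients. Replacement in C.11 is a recruitment instruction. The counts of 144 tests and 9 per sequence read as planning figures.
- **That 15% of washouts outlast an hour.** B.3 reports two patients, of 13 who completed HFOx, with low scores up to 1 hour after stopping: 2/13 = 15.4% (95% CI 1.9% to 45.4%). That followed two hours of HFOx, not 10 minutes, in mainly hypoxemic patients, and up to 1 hour is not beyond it. Taking it as r would put the washout mean 34% short if long washouts were dropped. If exits followed improvement only, a completers-only HFOx mean change would be 25% short, or the contrast 11% short if only high flow caused exits. The 25% case needs 52.9 starters for 36 finishers, or 36/52.9 = 68% completion from this one exit reason, against at least 80% for all reasons in A.2. It also ignores exits through worsening.

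**Conclusion.** The washout point holds as a cheap improvement to a secondary analysis. D.1's linear model does not fit data cut at 60 minutes, and either simple handling of the cut washouts biases the mean duration downward. The bias is negligible at a mean of about 10 minutes, 8% or 2% at r = 2%, and 16% or 5% at r = 5% (dropped or entered as 60). These figures rest on the exponential assumption and on an r that the documents do not supply. The direction does not depend on either, provided some washouts reach the limit.

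The primary analysis is not shown to be at fault. It lacks one sentence on exited patients' data. Even a completers-only analysis would, with exits in both directions, shift the HFOx mean change by about 1% at r = 2% and 12% at an implausible far end, and the HFOx minus LFAir contrast by at most about 5%, under the assumed means and SDs. These shifts are well inside one standard error. The completion-rate definition, with all starters as denominator, is not in question.

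**What to change.** Keep the 1-hour limit and amend D.1.

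1. Replace the linear model for washout duration with a time-to-event or censored-regression model with a patient random effect. Treat washouts that reach 60 minutes, and those cut short by withdrawal or rescue medication, as right-censored at the last assessment. For the 60-minute cut the censoring time is fixed by design; for withdrawal and rescue the analysis has to assume that censoring is unrelated to the remaining duration, and the report should say so.
2. As a minor clarification, state that periods observed before a C.11 exit stay in the primary mixed model, excluding NRS scores taken after rescue medication, and that replacements are added rather than substituted. Say whether 36 means starters or finishers.
3. Tabulate C.11 exits by reason, direction (below or above baseline) and preceding intervention.

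The cost is a few sentences, one small table from data already collected, and slightly more analysis work for the censored model. No patients are needed beyond the replacements that C.11 already requires. Sequence numbers may become unequal, which the mixed model handles.
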